1.4. Dose Rationale

The initial first-in-human dose for Part A (SAD) was 0.5 mg/kg. This did not exceed the maximum recommended starting dose (MRSD) using a safety factor of 10.

The MRSD is based on the 13-week rat and dog Good Laboratory Practice (GLP) studies evaluating doses of 50, 200, and 1000 mg/kg/day in rats and 50, 200, and 400 mg/kg/day in dogs.

AT-007 was administered to Beagle dogs once daily (QD) for at least 91 consecutive days via oral gavage. The following parameters and endpoints were evaluated in this study: clinical signs, body weights, body weight gains, food consumption, ophthalmology, electrocardiography, clinical pathology parameters (hematology, coagulation, serum chemistry, and urinalysis), toxicokinetic parameters, gross necropsy findings, organ weights, and histopathologic examinations.

There were no test article-related changes for ophthalmology, electrocardiography, clinical pathology, or organ weight data throughout the study.

Administration of AT-007 by once daily oral gavage was well tolerated in dogs at levels of 50, 200, and 400 mg/kg/day. The early termination (Day 85) in 1 male dog from the 400 mg/kg/day was associated with hematopoietic changes that were not observed in any other male or female dog at any dose level; as such, this observation was considered sporadic and a relationship with the test-article could not be established.

Therefore, the no-observed-adverse-effect level (NOAEL) was considered to be 400 mg/kg/day. This dosage corresponded to mean AUC_{0-24} values of 1,130,000 and 1,160,000 h*ng/mL on Day 91 for males and females, respectively, and C_{max} values of AT-007 of 145,000 and 155,000 ng/mL on Day 91 for males and females, respectively.

In the 13-week rat toxicology study, doses of 50, 200, and 1000 mg/kg/day were administered QD for 91 consecutive days via oral gavage. The following parameters and endpoints were evaluated in this study: clinical signs, body weights, body weight gains, food consumption, ophthalmology, clinical pathology parameters (hematology, coagulation, clinical chemistry, and urinalysis), toxicokinetic parameters, gross necropsy findings, organ weights, and histopathologic examinations.

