There were no control or test article-related clinical observations or significant effects on body weights, food consumption, ophthalmology, clinical pathology, or mortality findings throughout the study. All gross necropsy and histopathological findings for the main and recovery periods resulted in no evidence of test article-related effects. Therefore, the NOAEL in the rat was considered to be 1000 mg/kg/day. This dosage corresponded to mean AUC_{0-24} values of 2,040,000 and 2,360,000 h*ng/mL on Day 90 for males and females, respectively, and C_{max} values of AT-007 of 182,000 and 306,000 ng/mL on Day 90 for males and females, respectively.

Based on the NOAEL of 1000 mg/kg in rats and the NOAEL of 400 mg/kg in dogs, the human equivalent doses (HEDs) were calculated to be the following: 160 mg/kg/day from the rat and 216 mg/kg/day from the dog. Because the NOAEL of 400 mg/kg/day in dogs is the lower of the two, the HED of 216 mg/kg/day was chosen for the derivation of the MRSD. Therefore, using

the default safety factor of 10, the MRSD for AT-007 is 21.6 mg/kg/day. After consideration of other factors related to known pharmacology and another significant clinical program in the same mechanistic class, the starting dose for AT-007 in Part A was 0.5 mg/kg/day. This equates to a safety margin of 432 (216/0.5).

Dose levels in Part A escalated from 0.5 mg/kg to 5 mg/kg, 10 mg/kg, 20 mg/kg, and 40 mg/kg in the 5 cohorts (Cohorts A1 through A5) with no dose-limiting toxicity (DLT) identified in any cohort.

The first 3 cohorts in Part B (Cohorts B1, B2, and B3) escalated from 5 mg/kg to 10 mg/kg to 20 mg/kg following acceptable results for the same doses in Part A. Cohort B4 will start with this version of the protocol (version 5.0) and use a dose of 40 mg/kg based on that dose being acceptable in Cohort A5. The study drug exposure results were carefully considered to ensure that the plasma concentrations measured in Part A were in the range to detect changes in AR activity and galactitol levels in subjects with CG.

The doses in Part C are based on those in Part B. Cohort C1 was conducted with the same dose as Cohort B2 (10 mg/kg). Cohort C2 used the dose as Cohort B3 (20 mg/kg). Cohort C3 will use the same dose as Cohort B4 (40 mg/kg).

The initial dose in Part D (5 mg/kg) was based on data from Part A (Cohorts A1 through A4) and Part B (first 2 cohorts).

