Table 9: PK Parameters of AT-007 During Multiple Dosing in Healthy Subjects (Parts B and C) and Subjects with Galactosemia (MAD Period of Parts D and E and Part D Extension)

PK Parameter	Definition
C_{max}	Maximum concentration, determined directly from individual concentration time data (Day 1 and Day of Last Dose)
T_{max}	Time of the maximum concentration (Day 1 and Day of Last Dose)
λ_z	The observed terminal rate constant; estimated by linear regression through at least 3 data points in the terminal phase of the log concentration-time profile (Day of Last Dose only)
$T_{1/2}$	The observed terminal half-life, calculated as: $T_{1/2} = \frac{\ln(2)}{\lambda_z}$ (Day of Last Dose only)
AUC_{tau}	Area under the concentration-time curve during the 24-hour dosing interval; calculated using the linear trapezoidal rule (Day 1 and Day of Last Dose) Note: If quantifiable data are not observed through 24 h postdose, AUC_{tau} will be estimated using extrapolation (from the time of the last reported concentration to 24 h) and AUC_{last} will also be reported.
AUC_{last}	Area under the concentration-time curve from time-zero to the time of the last quantifiable concentration; calculated using the linear trapezoidal rule (Day of Last Dose; Day 1 if quantifiable data are not observed through 24 h postdose)
AUC_{inf}	Area under the concentration-time curve from time-zero extrapolated to infinity; calculated as: $AUC_{inf} = AUC_{last} + \frac{C_{last}}{\lambda_z}$ (Day of Last Dose only)
$AUC_{Extrap} (\%)$	The percentage of AUC_{inf} based on extrapolation (Day of Last Dose only)
C_{last}	The last quantifiable concentration determined directly from individual concentration-time data (Day 1 and Day of Last Dose)
T_{last}	Time of the last quantifiable concentration (Day 1 and Day of Last Dose)
CL/F	Clearance after extravascular administration, calculated as: CL/F = Dose/ AUC_{tau} (Day X), where Day X = Day of Last Dose and Dose is the actual dose administered (mg/kg x kg). (Day of Last Dose only) Note: CL/F/kg may also be reported
Vz/F	Volume of distribution in the terminal phase, calculated as: Vz/F = (CL/F)/ λ_z (Day of Last Dose only) Note: Vz/F/kg may also be reported

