Rac	The accumulation ratio during multiple dose administration, based on C_{max} and AUC_{tau} ; calculated as: Rac (AUC_{tau}) = AUC_{tau} (Day X) / AUC_{tau} (Day 1) Rac (C_{max}) = C_{max} (Day X) / AUC_{tau} (Day 1) Note: Rac will be tabulated with the pharmacokinetic parameters on Day X. Note: Day X = Day of Last Dose

Note: Day of Last Dose is Day 7 in Parts B and C, Day 32 in the MAD portion of Parts D and E, and Day 90 in Part D Extension.

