| Rac | The accumulation ratio during multiple dose administration, based on C_{max} and AUC_{tau} ; calculated as: Rac $(AUC_{tau}) = AUC_{tau}$ $(Day X) / AUC_{tau}$ $(Day 1)$ Rac $(C_{max}) = C_{max}$ $(Day X) / AUC_{tau}$ $(Day 1)$ Note: Rac will be tabulated with the pharmacokinetic parameters on Day X. Note: Day $X = Day$ of Last Dose | |

Note: Day of Last Dose is Day 7 in Parts B and C, Day 32 in in the MAD portion of Part D and E, and Day 90 in Part D Extension

Urine concentration data from Part A4, A5 and Part D3 will be used to determine the following parameters:

Ae Amount excreted into urine, calculated over 72 hours

Fe% Fraction of drug excreted in urine over 72 hours, calculated as Ae/dose X

100%

Only data points that describe the terminal elimination log-linear decline will be used in the regression equation for calculation of terminal elimination phase rate constant; C_{max} and any data point in the distribution phase are not included in the calculation. A minimum of 3 points will be used for determination of the terminal elimination phase rate constant. A general rule of adjusted $R^2 > 0.80$ will be considered as acceptable for calculation of the terminal elimination phase rate constant. If the adjusted R^2 falls below 0.80, then the terminal elimination phase rate constant will be reported as not determined (ND) and that subject's λ_z , $t_{1/2}$, AUC_{inf} , CL/F, and Vz/F will be reported as ND in the appropriate listings. If the extrapolated AUC_{inf} is more than 20%, then AUC_{inf} , CL/F and Vz/F will be listed but excluded from descriptive summaries and statistical analysis.

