7.10 Analysis of Pharmacokinetic Data

Plasma and urine PK parameters of AT-007 (including metabolites if determined) will be summarized by dose level and part using descriptive statistics. CSF concentration of AT-007 for cohort C1, C2 and C3 will be summarized by Cohort.

The PK Population will be used for all listings, concentration summaries, PK summaries and statistical analysis. The individual sampling and subject concentration-time for plasma and CSF concentrations will be listed and displayed graphically (plasma only) on linear and semi-log scales. The plasma and CSF drug concentrations will be summarized descriptively by nominal time point, Part and Cohort in tabular and graphical (plasma only) formats (linear and semi-log scales). The amount of AT-007 in urine will be listed by subject and summarized by nominal collection interval, Part and Cohort. Summary statistics will include: n, arithmetic mean, standard deviation (SD), coefficient of variation (CV%), median, minimum, maximum, and geometric mean (GM).

Pharmacokinetic parameters for AT-007 will be listed and summarized descriptively by Part, Cohort and Day, including n, arithmetic mean, SD, minimum, median, maximum, CV(%),GM, geometric SD, geometric CV%; geometric CV% calculated as the square root of the exponentiated SD of the natural log transformed data (SQRT(exp(sln^2)-1)), where appropriate. For t_{max} , only n, minimum, median, and maximum will be reported.

The dose proportionality of the primary PK parameters, AUC_{last} , AUC_{inf} and C_{max} after single dose (Part A, Part D and E, single dose portion) and AUC_{tau} , and C_{max} for single and multiple doses, over the administered dose range will be investigated using the following power model,

log(PK parameter) = a + b * log(dose), where a is the intercept and b is the slope.

Dose proportionality will be assessed for each part of the study separately. Furthermore, pooling of data across all parts at same dose level may be used to access overall dose proportionality for the entire range of the administered doses. However, pooling will be based on either the Day 1 dose or following multiple doses.

Each log-transformed PK parameter will be fit with a power model with a fixed effect term for log-transformed dose. For each PK parameter, the slope and associated 90% CI will be presented. A minimum of 3 values per dose cohort must be available for a given parameter to estimate dose proportionality with the power model.

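### The Cmax accumulation ratio is defined with Day 1 AUCtau as its denominator, so it carries units of 1/h and does not measure accumulation

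*Protocol*

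**What the plan says.** Protocol section 7.2, Table 9, lists an accumulation ratio, Rac, for AUCtau and for Cmax. The AUCtau version divides the last-dose-day value by the Day 1 value of the same quantity. The Cmax version is given as "C_{max} (Day X) / AUC_{tau} (Day 1"). SAP section 6.1.1, Table 6-2, repeats it: "Rac $(C_{max}) = C_{max}$ $(Day X) / AUC_{tau}$ $(Day 1"). SAP section 4, which lists departures from the protocol, does not mention Rac.

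The same tables already plan Cmax on both days: "Maximum concentration, determined directly from individual concentration time data (Day 1 and Day of Last Dose"). SAP section 7.10 adds that "Pharmacokinetic parameters for AT-007 will be listed and summarized descriptively by Part, Cohort and Day".

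The paragraph after Table 6-2 in SAP 6.1.1 sets two exclusion rules:

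- If the terminal fit has adjusted R-squared below 0.80, CL/F is reported as not determined, together with lambda-z, half-life, AUCinf and Vz/F.
- If more than 20% of AUCinf is extrapolated, AUCinf, CL/F and Vz/F are listed but left out of summaries and statistical analysis.

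Neither rule is limited to single dosing. Single-dose CL/F is Dose/AUCinf (Protocol Table 8, SAP Table 6-1). Multiple-dose CL/F is Dose/AUCtau on the day of last dose (Protocol Table 9, SAP Table 6-2).

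**The concern.** An accumulation ratio compares the same exposure measure after repeated and after first dosing. It must be dimensionless and must equal 1 if the profile repeats unchanged. The written Cmax formula meets neither condition, and its value changes with the time unit used for AUC. PK parameters are a secondary endpoint, and both tables say Rac will be tabulated with the last-day parameters. A programmer who follows the SAP will therefore report wrong numbers, and one who silently corrects the formula departs from both controlling documents.

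The CL/F wording raises a separate, smaller concern. Read literally, a poor terminal fit or a large extrapolated tail would remove multiple-dose CL/F values from the results even where AUCtau was fully observed over 24 h and neither lambda-z nor AUCinf entered the calculation.

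**Working it through.** The plan states no numerical Rac, so there is no figure to reproduce. The check is on the formula.

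**1. Units.** In Protocol section 1.4, Cmax is in ng/mL and AUC in h*ng/mL. The written quotient is therefore (ng/mL)/(h*ng/mL) = 1/h.

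**2. No-accumulation test on the documents' own figures.** If Day X repeats Day 1 exactly, Rac must be 1. The written formula then reduces to Cmax/AUC on one profile. Inputs from Protocol 1.4 are dog AUC0-24 "values of 1,130,000 and 1,160,000 h*ng/mL on Day 91 for males and females", dog Cmax "values of AT-007 of 145,000 and 155,000 ng/mL on Day 91 for males and females", rat AUC0-24 "values of 2,040,000 and 2,360,000 h*ng/mL on Day 90 for males and females" and rat Cmax "values of AT-007 of 182,000 and 306,000 ng/mL on Day 90 for males and females".

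| Group | Cmax/AUC0-24 | Written value, per h | Correct value |
|---|---|---|---|
| Dog, male | 145,000/1,130,000 | 0.128 | 1 |
| Dog, female | 155,000/1,160,000 | 0.134 | 1 |
| Rat, male | 182,000/2,040,000 | 0.089 | 1 |
| Rat, female | 306,000/2,360,000 | 0.130 | 1 |

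Expressed per day, each written value would be 24 times larger. These are group means in animals. They show how the formula behaves and do not predict human accumulation.

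**3. Does the written value at least track accumulation?** This step rests on assumptions that are not in the documents: a one-compartment oral model, ka 0.5, 1, 1.5 and 3 per h, half-life 4, 8, 12 and 24 h, a 24 h interval, and 7 doses (Parts B, C) or 27 doses (Parts D, E), with doses superposed.

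- Over the whole grid, the true Cmax ratio is 1.02 to 2.09 and the written formula gives 0.083 to 0.150 per h.
- At the nominal sampling times to 24 h with linear trapezoids, the ranges are 1.02 to 2.08 and 0.081 to 0.145 per h.
- At ka 1/h with 7 doses:

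| Half-life, h | True Cmax ratio | Written value, per h |
|---|---|---|
| 4 | 1.019 | 0.125 |
| 8 | 1.157 | 0.092 |
| 12 | 1.357 | 0.090 |
| 24 | 2.025 | 0.109 |

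- At ka 3/h, going from a 4 h to a 12 h half-life, the true ratio rises from 1.02 to 1.34 while the written value falls from 0.150 to 0.096 per h.

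The written value is therefore not a rescaled accumulation ratio. It can move in the opposite direction.

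**4. Is the right denominator available?** Yes. Day 1 is densely sampled in Parts B, C, D and E (Protocol Appendices B to E). In Parts D and E no PK sample is scheduled on Day 6, the first day of multiple dosing, so Day 1 is read as the single-dose day. The Part D Extension is different: its only Day 1 PK sample is predose (Protocol Appendix F, footnote n; SAP 3.1.7). Neither Rac nor the other Day 1 parameters can be computed there from the Extension's own data, even with the formula corrected.

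**5. How many profiles.** Planned active profiles are B 6+4+6+4 = 20, C 3x4 = 12, D 3x4 = 12 and E 4 to 12. The total is 20+12+12+4 = 48 to 20+12+12+12 = 56.

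**6. The CL/F rules.** Multiple-dose CL/F = Dose/AUCtau. With AUCtau observed to 24 h, neither lambda-z nor AUCinf appears in it. Under mono-exponential decline the extrapolated fraction is exp(-lambda-z x T), which exceeds 20% when half-life is above T x ln2/ln5. That is about 20.7 h for last-dose sampling to 48 h (Parts B to E) and about 10.3 h for sampling to 24 h (Extension). The documents give no human half-life, so how often either rule would apply is unknown.

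**The case against.** The strongest reply is that the intent is plain. The row describes an accumulation ratio based on Cmax and on AUCtau, the AUCtau version beside it is like over like, and a pharmacokineticist would probably recognise a copying slip when values near 0.1 appeared. That is fair, and it limits the likely harm. It does not make the formula right, because it is the operative definition in both documents and nothing else in them corrects it.

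Three stronger readings are tempting, and the documents do not support them.

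- A reader might infer that every subject's result is wrong. Placebo subjects are outside the PK population, and the error occurs only if the formula is programmed literally. The count of 48 to 56 is also nominal: Part D and E cohorts may grow to 8, and cohorts above 40 mg/kg may be added.
- A reader might infer that dose decisions or the main PK conclusions are compromised. The stopping criteria in Protocol 3.5 rest on dose-limiting toxicities and on fatal or life-threatening events. The power model in SAP 7.10 uses AUC and Cmax. Neither uses Rac. The Sponsor does review PK data, but no stated rule depends on this ratio.
- A reader might infer that the 20% rule should also be lifted from multiple-dose Vz/F, since Vz/F = (CL/F)/lambda-z contains no AUCinf. That does not follow. Vz/F needs a well-captured terminal phase, a large extrapolated tail is a reasonable warning that it was not captured, and excluding Vz/F then is a defensible quality rule.

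On CL/F, the objection that values failing the 20% rule are still listed is correct. They are missing only from summaries and analysis. The R-squared rule goes further and reports them as not determined.

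**Conclusion.** The Cmax accumulation ratio is wrong as written in both documents. That conclusion rests on units alone and needs no model; the one-compartment figures only illustrate it. If followed literally, the formula gives a wrong tabulated value for each AT-007-treated subject with a PK profile in Parts B, C, D and E, nominally 48 to 56 active profiles. The consequence is limited. This is a descriptive secondary parameter, Rac for AUCtau is correct, and the right ratio can be recovered from Day 1 and last-day Cmax. It should be fixed before outputs are programmed, but it does not threaten the trial's primary conclusions.

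The secondary point holds for multiple-dose CL/F only, and its practical size cannot be stated without a human half-life.

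**What to change.** - In Protocol Table 9 and SAP Table 6-2, write Rac(Cmax) = Cmax(Day X)/Cmax(Day 1).
- In SAP 6.1.1, state that the 20% extrapolation exclusion does not apply to multiple-dose CL/F, and that multiple-dose CL/F is not set to not determined for adjusted R-squared below 0.80 when AUCtau is observed to 24 h. Leave both rules unchanged for Vz/F, and the R-squared rule unchanged for lambda-z, half-life and AUCinf.
- Note under both tables that Day 1 parameters and Rac are not computed in the Part D Extension.

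The cost is one formula in each of two tables, one clause in one SAP paragraph and a table note. No new samples or data are needed. Each multiple-dose CL/F needs a flag showing whether AUCtau was observed or extrapolated.

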7.3. Assessments of Biomarkers of Galactose Metabolism

In Parts D, E, and D Extension, blood samples for the analysis of galactose and galactose metabolites including galactitol and galactose-1-phosphate, and urine samples for the analysis of galactitol will be collected at the visits as indicated in the Schedules of Assessment ([Appendix D](#), [Appendix E](#), and [Appendix F](#), respectively). Instructions for collecting and processing blood and urine samples for these biomarkers will be provided in a separate laboratory manual. Blood and urine samples will be analyzed for the levels of galactose (in plasma and urine), and galactose metabolites including galactitol (in plasma and urine), and galactose-1-phosphate (erythrocytes) using qualified or validated assays.

8. ADVERSE EVENTS

Subjects will be monitored for AEs from the signing of informed consent through the EOS (or EOE) Visit. The Investigator or a medically qualified designee will review each event. The Investigator or designee will assess its relationship to the study drug. Each AE will be graded for severity, and the date and time of onset and cessation will be recorded along with any treatment given for the AE and any action taken with regard to the study drug. Treatment of any AE will be evaluated and managed by a physician, either at the study site or at a nearby hospital or emergency room, as appropriate. The AE resolution or outcome will be recorded. All non-serious AEs will be reported on a regular basis or as specified by the Sponsor.

8.1. Definitions

8.1.1. Adverse Event (AE)

An AE is defined as any untoward medical occurrence associated with the use of a drug in humans, whether or not considered drug related.

An AE can be any unfavorable and unintended sign (e.g., an abnormal laboratory finding), symptom, or disease temporally associated with the use of a drug, without judgment to causality. An AE can arise from any use of the drug (e.g., off-label, use in combinations with another drug) and from any route of administration, formulation, or dose, including an overdose. AEs may include the onset of new illness and the exacerbation of pre-existing conditions. New signs and symptoms of underlying disease, or signs and symptoms of emerging disease must be recorded as AEs.

The Investigator/designee should attempt to establish a diagnosis of the event based on signs, symptoms, and/or other clinical information. In such cases, the diagnosis should be documented as the AE and not the individual signs/symptoms.

8.1.2. Serious Adverse Event (SAE)

A SAE is an AE that meets one or more of the following criteria:

- Results in death
- Is life-threatening (i.e., a subject is at immediate risk of death at the time of the event, not an event where occurrence in a more severe form might have caused death)
- Requires hospitalization or prolongation of existing hospitalization
- Results in persistent or significant disability or incapacity
- Is a congenital anomaly or birth defect
- Is an important medical event that may jeopardize the subject or may require a medical or surgical intervention to prevent one of the outcomes listed above

Examples of “important medical events” that are SAEs include allergic bronchospasm requiring intensive treatment in an emergency room or at home, blood dyscrasias, or convulsions that do not result in in-patient hospitalization.

The term "severe" is often used to describe the severity of a specific event (as in mild, moderate, or severe); the event itself, however, may be of relatively minor medical significance (such as severe headache). This is not the same as "serious," which is based on subject/event outcome or action criteria usually associated with events that pose a threat to a subject's life or functioning as defined by the criteria above.

During the study, if a subject has a hospitalization or procedure (e.g., elective surgery) that was scheduled before the study entry (i.e., before informed consent for an event/condition that occurred before the study), then the hospitalization is considered a therapeutic intervention and not the result of a SAE. However, if the event/condition worsens during the study, it should be reported as an AE (or SAE, if the event/condition results in a serious outcome such as prolongation of hospitalization).

